10.5 Other Safety Parameters

10.5.1 Abnormal Involuntary Movement Scale (AIMS)

Descriptive statistics for AIMS total score at baseline and changes from baseline at each assessment visit (including the end of the double-blind treatment period) will be presented by treatment group for the Safety Population.

10.5.2 Barnes Akathisia Rating Scale (BARS)

Descriptive statistics for BARS total score at baseline and changes from baseline at each assessment visit (including the end of the double-blind treatment period) will be presented by treatment group for the Safety Population.

10.5.3 Simpson-Angus Rating Scale (SAS)

Descriptive statistics for SAS total score at baseline and changes from baseline at each assessment visit (including the end of the double-blind treatment period) will be presented by treatment group for the Safety Population.

Confidential Page 35 of 72

PCS = potentially clinically significant; QTc = corrected QT interval; QTcB = QT interval/ $(RR)\frac{1}{2}$; QTcF = QT interval/ $(RR)\frac{1}{2}$.

10.5.4 Columbia-Suicide Severity Rating Scale (C-SSRS)

The number and percentage of patients with suicidal ideation or suicidal behavior as recorded on the C-SSRS will be tabulated by treatment group for lifetime history (at the Screening Visit), baseline, double-blind treatment period, and SFU Period for the Safety Population. Baseline of C-SSRS for each patient is defined as the last non-missing pre-treatment 'since last visit' assessment. The distribution of responses for the most severe suicidal ideation and most severe suicidal behavior will be presented by treatment group.

The severity of suicidal ideation will be presented in a decreasing order:

- Active suicidal ideation with specific plan and intent
- Active suicidal ideation with some intent to act, without specific plan
- Active suicidal ideation with any methods (not plan) without intent to act
- Non-specific active suicidal thoughts
- Wish to be dead

The severity of suicidal behavior will be presented in a decreasing order:

- Completed Suicide (for double-blind treatment period and for SFU period only)
- Actual attempt
- Interrupted attempt
- Aborted attempt
- Preparatory acts or behavior

For each analysis period (lifetime, baseline, double-blind treatment period, and SFU Period), each patient will be counted only once for suicidal ideation and for suicidal behavior, based on the most severe suicidal ideation and the most severe suicidal behavior reported during each specific period. A listing of patients with suicidal ideation or suicidal behavior will be provided. A listing of all AEs for patients with suicidal ideation or suicidal behavior will also be provided.

In addition, the number and percentage of patients with the following emergence of suicidal ideation or of suicidal behavior during the treatment period will be tabulated by treatment group for the Safety Population:

- Emergence of suicidal ideation (no suicidal ideation at Baseline, and any type of suicidal ideation post-Baseline)
- Emergence of serious suicidal ideation (no suicidal ideation at Baseline, and any serious suicidal ideation [Active suicidal ideation with specific plan and intent, or Active suicidal ideation with some intent to act, without specific plan] post-Baseline)
- Worsening of suicidal ideation (most severe suicidal ideation post-Baseline was more severe than it was at Baseline)
- Emergence of suicidal behavior (no suicidal behavior at Baseline, and any type of suicidal behavior post-Baseline)

Confidential Page 36 of 72

11.

Confidential Page 37 of 72

12.

Confidential Page 38 of 72

13.		

Confidential Page 39 of 72

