6.3.2 Exclusion Criteria

Patients who meet any of the following exclusion criteria will not be eligible to participate in the study.

Psychiatric Criteria:

- 1. Within the patient's lifetime, has a confirmed DSM-5 psychiatric diagnosis other than MDD, including:
 - a. Schizophrenia, Schizoaffective Disorder, Schizophreniform Disorder or other psychotic disorder;
 - b. Bipolar Disorder.
- 2. Within 6 months of Screening, has a confirmed DSM-5 psychiatric diagnosis other than MDD, including:
 - a. Anxiety disorders such as Panic Disorder or Generalized Anxiety Disorder; Obsessive-compulsive Disorder; Posttraumatic Stress Disorder as primary diagnoses. *Note*: anxiety symptoms may be allowed if secondary to MDD, provided these symptoms do not require concurrent treatment;
 - b. Eating disorder;
 - c. Substance use disorders (excluding nicotine)
 - d. Personality disorder of sufficient severity to have a major impact on the patient's psychiatric status;
 - e. Within 12 months of Screening, has had any other psychiatric condition (other than MDD) that has been the main focus of treatment.
- 3. The patient experiences a ≥ 25% decrease in the MADRS total score between Screening (Visit 1) and Baseline (Visit 2);
- 4. The patient experiences a ≥ 25% decrease in the QIDS-SR-16 total score between Screening (Visit 1) and Baseline (Visit 2);
- 5. In the opinion of the Investigator, the patient has a significant risk for suicidal behavior during his/her participation in the study or
 - a. At Screening (Visit 1), the patient scores "yes" on Suicidal Ideation Items 4 or 5 of the C-SSRS within 6 months prior to Screening or, at Baseline (Visit 2), the patient scores "yes" on Suicidal Ideation Items 4 or 5 since the Screening Visit;
 - b. At Screening (Visit 1), the patient has had 1 or more suicidal attempts within the 2 years prior to Screening; or
 - c. At Screening (Visit 1) or Baseline (Visit 2), the patient scores ≥ 5 on MADRS Item 10 (Suicidal Thoughts); or
 - d. The patient is considered to be an imminent danger to him/herself or others.
- 6. The patient has a first MDE at age 60 years or older.

Treatment Criteria:

- 7. In the current MDE, the patient has had > 2 ADTs administered at adequate dose (per product label) and for an adequate duration (at least 6 weeks);

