8.3.7 Columbia–Suicide Severity Rating Scale (C-SSRS)

The C-SSRS is a clinician-rated instrument that reports the severity of both suicidal ideation and behavior (Posner, 2011). The C-SSRS will be completed by a Sponsor-approved rater.

Suicidal ideation is classified on a 5-item scale:

- 1. Wish to be dead
- 2. Nonspecific active suicidal thoughts
- 3. Active suicidal ideation with any methods [not plan] without intent to act
- 4. Active suicidal ideation with some intent to act, without specific plan; and
- 5. Active suicidal ideation with specific plan and intent.

The C-SSRS also captures information about the intensity of ideation, specifically the frequency, duration, controllability, deterrents, and reasons for the most severe types of ideation.

Suicidal behavior categories are:

- Completed suicide
- Actual attempt
- Interrupted attempt
- Aborted attempt, and
- Preparatory acts or behavior

More than 1 classification can be selected provided it represents separate episodes. For actual attempts only, the actual or potential lethality is classified for the initial, most lethal, and most recent attempts.

The C-SSRS will be completed at all study visits. At Screening (Visit 1), the C-SSRS will be completed for the patient's lifetime history of suicidal ideation and behavior ("Baseline/Screening" version). At all other visits, the C-SSRS will be completed for suicidal ideation and behavior since the previous visit ("Since Last Visit" version). Before the patient leaves the study site, the Investigator or appropriately qualified designee will assess the patient's C-SSRS results.

The patient should not be released from the study center until the results of the C-SSRS are reviewed and the patient is not considered to be at risk. If there is doubt about whether a patient is at risk, the Investigator must obtain appropriate psychiatric consultation. The results of the C-SSRS will be recorded in the eCRF. The C-SSRS will be completed by a trained and Sponsor-approved rater.

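### Does the SAP's row for emergent serious suicidal ideation hide patients who already had milder ideation at Baseline?

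*SAP*

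**What the plan says.** SAP Section 10.5.4 takes as C-SSRS baseline the last pre-treatment form of the since-last-visit type: "Baseline of C-SSRS for each patient is defined as the last non-missing pre-treatment 'since last visit' assessment". Protocol Section 8.3.7 explains what that form covers: "At all other visits, the C-SSRS will be completed for suicidal ideation and behavior since the previous visit".

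The section then plans two kinds of display.

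- **Distribution by period.** "The distribution of responses for the most severe suicidal ideation and most severe suicidal behavior will be presented by treatment group". Lifetime, baseline, double-blind and safety follow-up periods are kept apart, and within each period a patient is counted once, at the most severe level reported. Patients with ideation or behaviour are also listed, as are their adverse events.
- **Change rows.** Four rows cover "emergence of suicidal ideation or of suicidal behavior during the treatment period will be tabulated by treatment group for the Safety Population". They are emergence of any ideation, emergence of serious ideation, worsening of ideation, and emergence of behaviour. The serious row is "Emergence of serious suicidal ideation (no suicidal ideation at Baseline, and any serious suicidal ideation" after Baseline, where serious means the two top levels (some intent to act; specific plan and intent). The worsening row is "Worsening of suicidal ideation (most severe suicidal ideation post-Baseline was more severe than it was at Baseline".

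On entry, Protocol Section 6.3.2, exclusion 5a, removes patients who at Baseline answer yes "on Suicidal Ideation Items 4 or 5 since the Screening Visit". It names no lower level.

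**The concern.** The row's label suggests a count of everyone who newly developed serious ideation on treatment. Its Baseline condition is stricter than that: it asks for no ideation of any level, not merely no serious ideation. A trial in depressed patients can be expected to enrol some people with a wish to be dead or non-specific suicidal thoughts, and exclusion 5a lets them in. If one of them progresses to ideation with intent, a reader would call that emergent serious ideation, yet the row leaves it out.

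Suicidality on the C-SSRS is part of the safety objective in Protocol Section 5.2. A row that understated new serious ideation, with nothing else in the output to correct it, would be a real weakness in the safety reporting.

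**Working it through.** The plan gives no figure to reproduce here, so the check is to apply each definition to every possible patient path.

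**Inputs**

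- Ideation levels run from 1 to 5 (Protocol 8.3.7); write 0 for none. Levels 4 and 5 are serious (SAP 10.5.4).
- Possible Baseline levels for an eligible patient: 0, 1, 2, 3. The baseline form looks back to the previous visit, normally Screening, and exclusion 5a bars levels 4 and 5 over that time.
- Possible most severe level after Baseline: 0 to 5.

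**Enumeration.** There are 4 × 6 = 24 pairs of Baseline and worst later level.

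| Display | Pairs that count | Number |
|---|---|---|
| Any move to level 4 or 5 | 4 Baseline levels × 2 | 8 |
| Serious-emergence row | 0→4, 0→5 | 2 |
| Moves to 4 or 5 left out of that row | 1→4, 1→5, 2→4, 2→5, 3→4, 3→5 | 6 |
| Emergence of any ideation | 0→1 to 0→5 | 5 |
| Worsening, read literally | 5 + 4 + 3 + 2 | 14 |

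All 6 omitted moves fall under worsening. If worsening is read as excluding patients with no ideation at Baseline, it holds 14 − 5 = 9 moves. Of these, 6 end at level 4 or 5 and 3 do not (1→2, 1→3, 2→3). On either reading the worsening row contains the omitted patients but does not separate them from smaller increases.

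**What the distribution adds.** These are types of move, not numbers of patients. For patient counts, within one arm let

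- Z = patients going from 0 to level 4 or 5,
- L = patients going from levels 1–3 to level 4 or 5.

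Then

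- serious-emergence row = Z;
- double-blind distribution, level 4 line plus level 5 line = Z + L, because each patient is counted once and nobody eligible starts at 4 or 5;
- difference = (Z + L) − Z = L.

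If the row were instead conditioned on no serious ideation at Baseline, it would show Z + L. That number is already in the planned output, by arm. The omitted group L follows from one subtraction between two displays in the same section. The baseline distribution also shows how many patients in each arm began at levels 1 to 3.

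**Size.** The documents give neither the share of patients at Baseline levels 1–3 (p) nor their risk of reaching level 4 or 5 relative to patients with none (r). The share of new serious cases outside the row would be p·r / [(1 − p) + p·r]. On purely assumed inputs:

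| | p = 0.1 | p = 0.3 | p = 0.5 |
|---|---|---|---|
| r = 1 | 10% | 30% | 50% |
| r = 3 | 25% | 56% | 75% |

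At r = 1 the formula simply returns p. The table shows that the gap between the row and the distribution could be visible. It says nothing about what this trial would find, and whatever the gap is, the distribution displays it.

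**The case for a change.** The best case for the concern is about how the row will be read. Suicidality is a named safety objective, and a line headed as emergent serious ideation is the kind that gets lifted out alone. In the other two emergence rows the Baseline condition is absence of the very thing that emerges: no ideation then any ideation, no behaviour then any behaviour. Only the serious row requires absence of a broader class, which makes it a strict subset of emergence of any ideation. The SAP does not explain the choice, and a reader who wants the full count must know that exclusion 5a keeps Baseline levels 4 and 5 out, then reconcile two displays.

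Part of this stands. Read alone, the row can be lower than the level 4 and 5 lines of the distribution. Section 10.5.4 also promises percentages for the Safety Population without saying whether the denominator is everyone or only patients who meet the Baseline condition.

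Neither point amounts to an error. The condition is written in the parenthesis beside the label, so nothing is concealed. The ideation rows follow a coherent scheme: a change from none is emergence, and an increase from existing ideation is worsening. Asking for no serious ideation at Baseline instead would be an equally legitimate definition, but the choice between the two is a preference. The documents contain no rule that the printed version breaks; SAP Sections 10.2 to 10.4 themselves use more than one baseline condition for their counts. The unstated denominator is a missing detail. SAP Section 2 places table specifications in a separate document, where such a detail could sit, though that document is not available to confirm it.

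**Conclusion.** The concern does not hold. The row does leave out eligible patients who go from levels 1–3 to level 4 or 5, but those patients appear in the double-blind distribution by arm, in the worsening row and in the patient listing. The distribution already carries the count that a redefined row would give, so no safety result or conclusion would change. The analysis is descriptive and has no bearing on power or type I error.

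The exact match between the distribution and a redefined row rests on three assumptions: patients meet exclusion 5a, they have a pre-treatment since-last-visit form, and the treatment period named for the change rows is the double-blind period used for the distribution. A patient enrolled with level 4 or 5 at Baseline, or without a baseline form, could make the two differ; a Baseline level of 4 or 5 would itself show in the baseline distribution. The number of patients in the omitted group cannot be worked out from the documents.

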14. STATISTICAL SOFTWARE

Statistical analyses of efficacy and safety parameters will be performed using version 9.4 (or newer) of $SAS^{\tiny{\circledR}}$.

Confidential Page 40 of 72

and Key

15. DATA HANDLING CONVENTIONS

a Relative to the date of the first dose of double-blind study treatment.

Table 15-4 presents the visits assigned for laboratory and ECG parameters to the range of treatment days (window) during which an actual visit may have occurred.

Confidential Page 42 of 72

b Visit day is calculated as visit date – date of the first dose of double-blind study treatment, + 1 day if the visit date is on or after the date of the first dose of double-blind study treatment.

Derived Visit	Scheduled Visit (Day ^a)	Window ^b	Target Day
Baseline	Week 0 (Day 1)	Days ≤ 1	Day 1
Week 3	Week 3 (Day 22)	Days [2, 32]	Day 22
Week 6	Week 6 (Day 43)	Days ≥ 33 and within double-blind treatment period	Day 43
End of double- blind treatment period	Final or termination visit during the double-blind treatment period		

- a Relative to the date of the first dose of double-blind study treatment.
- b Visit day is calculated as visit date date of the first dose of double-blind study treatment, + 1 day if the visit date is on or after the date of the first dose of double-blind study treatment.

Table 15-5 presents the visits assigned for AIMS, BARS, and SAS parameters to the range of treatment days (window) during which an actual visit may have occurred.

Table 15-5: Visit Time Windows for the Double-blind Treatment Period for AIMS, BARS and SAS Parameters

Derived Visit	Scheduled Visit (Day ^a)	Window ^b	Target Day
Baseline	Week 0 (Day 1)	Days ≤ 1	Day 1
Week 2	Week 2 (Day 15)	Days [2, 22]	Day 15
Week 4	Week 4 (Day 29)	Days [23, 36]	Day 29
Week 6	Week 6 (Day 43)	y 43) Days \geq 37 and within double-blind treatment period	
End of double- blind treatment period	Final or termination visit during the double-blind treatment period		

- a Relative to the date of the first dose of double-blind study treatment.
- b Visit day is calculated as visit date date of the first dose of double-blind study treatment, + 1 day if the visit date is on or after the date of the first dose of double-blind study treatment.

Handling of multiple records of safety assessments within the same analysis window is provided in Section 15.2.

15.2 Repeated or Unscheduled Assessments of Safety Parameters

If a patient has repeated assessments on or before the start of double-blind study treatment, then the results from the last assessment made before the start of double-blind study treatment will be used as baseline. For visits with postbaseline repeated or unscheduled assessments of laboratory parameters, the non-missing values of the scheduled assessment will be used for summary statistics. If the scheduled assessments are missing, the last value from repeated or unscheduled assessments within the analysis window will be used. If postbaseline repeated or unscheduled vital signs and/or ECGs occur, apply the time-window rule and select the last non-missing values for each visit or endpoint. All postbaseline assessments will be used for PCS value determination and will be presented in the data listings.

Confidential Page 43 of 72

15.3 Missing Date of Double-Blind Study Treatment

When the date of the last dose of double-blind study treatment taken during the double-blind treatment period is missing for a patient in the Safety Population, all efforts should be made to obtain the date from the Investigator. If it is still missing after all efforts, then the last known dose date will be set as the date of the last dose of double-blind study treatment.

15.4 Missing Severity Assessment for Adverse Events

If severity is missing for an AE that started before the date of the first dose of double-blind study treatment, then a severity of *mild* will be assigned. If the severity is missing for an AE that started on or after the date of the first dose of double-blind study treatment, then a severity of *severe* will be assigned. The imputed values for severity assessment will be used for the incidence summary; while the actual values will be presented in the data listings.

15.5 Missing Relationship to Investigational Product for Adverse Events

If the relationship to double-blind study treatment is missing for an AE that started on or after the first dose date of double-blind study treatment, a causality of *yes* will be assigned. The imputed values for relationship to double-blind study treatment will be used for the incidence summary, while the actual values will be presented in the data listings.

15.6 Missing Date Information for Adverse Events

The following imputation rules apply only to cases in which the start date is incomplete (ie, partially missing) for AEs.

Missing month and day

- If the year of the incomplete start date is the same as the year of the date of the first dose of double-blind study treatment, then the day and month of the date of the first dose of double-blind study treatment will be assigned to the missing fields;
- If the year of the incomplete start date is before the year of the date of the first dose of double-blind study treatment, then December 31 will be assigned to the missing fields;
- If the year of the incomplete start date is after the year of the date of the first dose of doubleblind study treatment, then January 1 will be assigned to the missing fields.

Missing month only

• If only the month of the incomplete start date is missing, the day will also be treated as missing, and both the month and day will be replaced according to the procedure described above.

Missing day only

• If the month and year of the incomplete start date are the same as the month and year of the date of the first dose of double-blind study treatment, then the day of the date of the first dose of double-blind study treatment will be assigned to the missing field;

Confidential Page 44 of 72

- If either the year of the incomplete start date is before the year of the date of the first dose of double-blind study treatment or if the years are the same but the month of the incomplete start date is before the month of the date of the first dose of double-blind study treatment, then the last day of the month will be assigned to the missing field;
- If either the year of the incomplete start date is after the year of the date of the first dose of double-blind study treatment or if the years are the same but the month of the incomplete start date is after the month of the date of the first dose of double-blind study treatment, then the first day of the month will be assigned to the missing field.

If the stop date is complete and the imputed start date, when imputed as instructed above, is after the stop date, then the start date will be imputed to equal the stop date.

If the start date is completely missing and the stop date is complete, then use the following algorithm to impute the start date:

- If the stop date is on or after the date of the first dose of double-blind study treatment, the date of the first dose of double-blind study treatment will be assigned to the missing start date;
- If the stop date is before the date of the first dose of double-blind study treatment, the stop date will be assigned to the missing start date.

15.7 Missing Date Information for Prior or Concomitant Medications

For prior or concomitant medications, including psychotropic medications, incomplete (ie, partially missing) start dates and/or stop dates will be imputed. If the start date and the stop date for a patient are both incomplete, the start date will be imputed first.

15.7.1 Incomplete Start Date

The following rules will be applied to impute the missing numeric fields. If the stop date is complete and the imputed start date is after the stop date, then the start date will be imputed using the stop date.

Missing month and day

- If the year of the incomplete start date is the same as the year of the date of the first dose of double-blind study treatment, then the month and day of the date of the first dose of double-blind study treatment will be assigned to the missing fields;
- If the year of the incomplete start date is before the year of the date of the first dose of double-blind study treatment, then December 31 will be assigned to the missing fields;
- If the year of the incomplete start date is after the year of the date of the first dose of double-blind study treatment, then January 1 will be assigned to the missing fields.

Confidential Page 45 of 72

Missing month only

• If only the month of the incomplete start date is missing, the day will also be treated as missing, and both month and day will be replaced according to the procedure described above.

Missing day only

- If the month and year of the incomplete start date are the same as the month and year of the date of the first dose of double-blind study treatment, then the day of the date of the first dose of study treatment will be assigned to the missing field;
- If either the year of the incomplete start date is before the year of the date of the first dose of double-blind study treatment or if the years are the same but the month of the incomplete start date is before the month of the date of the first dose of double-blind study treatment, then the last day of the month will be assigned to the missing field;
- If either the year of the incomplete start date is after the year of the date of the first dose of double-blind study treatment or if the years are the same but the month of the incomplete start date is after the month of the date of the first dose of double-blind study treatment, then the first day of the month will be assigned to the missing field.

